11.4.5 Abnormal Laboratory Findings and Other Abnormal Investigational Findings

Abnormal laboratory findings and other abnormal investigational findings (e.g. on an ECG trace) should not be reported as AEs unless they are associated with clinical signs and symptoms, lead to treatment discontinuation, or are considered otherwise medically important by the Investigator. If an abnormality fulfills these criteria, the identified medical condition (e.g. low white blood cell count, increased ALT) must be reported as the AE rather than the abnormal value itself.

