12.1.2 Safety and Tolerability

Safety and tolerability of tipifarnib will be assessed based on the following:

- Incidence, duration, and severity of treatment-emergent AEs, SAEs, AEs resulting in permanent discontinuation of study drug, and deaths within approximately 30 days from the last dose of study drug (or immediately before the administration of another anti-cancer treatment)
- Changes in laboratory test results
- Changes in vital signs including blood pressure, heart rate and temperature
- Changes in ECG results

AEs will be coded using the using version 22.0 of the Medical Dictionary for Regulatory Activities (MedDRA) and upversioned prior to database lock. Treatment-emergent AEs are defined as AEs that start on or after the first dose of study drug and within approximately 30 days of the last administration of study drug. AEs will be summarized by the number and percentage of subjects who experienced the event, according to system organ class and preferred term. A subject reporting multiple cases of the same AE will be counted once within each system organ class and similarly counted once within each preferred term.

Unless specified otherwise, the denominator for these calculations will be based on the number of subjects enrolled who received at least one administration of tipifarnib, irrespective of the total number of doses or treatment cycles administered. These conventions will be appropriately modified to calculate AE incidence rates separately for each cycle that study therapy is administered. AE incidence rates may also be calculated based on other measures of subject exposure (e.g., total number of treatment cycles administered). AEs will also be summarized by NCI CTCAE v5.0 severity grade and by relationship to each study drug. Additional summaries may also be provided for SAEs, and events resulting in the permanent discontinuation of therapy. All AEs will be included in individual subject listings.

The incidence of grade 3 and 4 hematological toxicities (including neutropenia, thrombocytopenia, and anemia) will be provided by treatment cycle and across all treatment cycles. The toxicity grades for laboratory tests will be based on NCI CTCAE v5.0. The use of blood transfusions (platelets, red blood cells) and/or growth factor support will be reported.

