### 9.8.1 Adverse Events

All summaries of AEs will be based on treatment-emergent AEs (TEAEs) unless otherwise indicated.

TEAE is defined as AE that starts on or after the first dose of the study drug and within 30 days of the last administration of the study drug.

Counting of AEs will be by subject, not by event; subjects will be counted only once within each SOC or PT.

The count and percentage of subjects who report TEAEs will be summarized for AIM-HN safety analysis set as follows:

TEAEs by SOC and PT

TEAEs by PT (Any Grade and Grade  $\geq$  3)

TEAEs by SOC, PT, and maximum NCI-CTCAE grade

Serious TEAEs by SOC and PT

TEAEs related to tipifarnib by PT (Any Grade and Grade  $\geq$  3)

TEAEs related to tipifarnib by SOC, PT, and maximum NCI-CTCAE grade

Serious TEAEs related to tipifarnib by SOC and PT

TEAEs leading to discontinuation of tipifarnib by SOC and PT

TEAEs with an outcome of death by SOC and PT

Non-Serious TEAE experienced by  $\geq$  5% of subjects by PT

For grade summaries, subjects with multiple events within a particular SOC or PT will be counted under the category of their most severe event within that SOC or PT. Events will be sorted by descending frequency by SOC, and by PT within SOC for summaries.

AEs will be listed for individual subjects, including information regarding onset, duration, severity, seriousness, outcome and relationship to study drug.

AEs will not be summarized by Cycle, except for Overall Summary and AEs by SOC and PT for Cycle 1.

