## 9.8.3 Clinical Laboratory Parameters

Clinical laboratory assessments (hematology and clinical serum chemistry) will be summarized descriptively based on observed values at baseline and each post-baseline scheduled visit and change from baseline. All laboratory results (hematology, clinical serum chemistry, urinalysis, and coagulation) will be reflected in listings.

Shift tables for some hematology and chemistry tests will be provided for the maximum post-baseline grade including data from any scheduled and unscheduled visits prior to or on end of treatment visit. These tables will compare the NCI-CTCAE grade for the baseline value relative to each post-baseline time point value for all non-missing post-baseline data. Subjects meeting shift criteria for high values as well as low values during the course of the trial will be summarized for both criteria.

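### The visible SAP does not carry forward the protocol's by-cycle Grade 3–4 haematological incidence or its transfusion and growth-factor summary, and leaves the graded laboratory tables to unnamed tests

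*SAP*

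**What the plan says.** Protocol 12.1.2 makes a specific commitment on blood toxicity: "The incidence of grade 3 and 4 hematological toxicities (including neutropenia, thrombocytopenia, and anemia) will be provided by treatment cycle and across all treatment cycles". It gives the grading basis, "The toxicity grades for laboratory tests will be based on NCI CTCAE v5.0", and adds: "The use of blood transfusions (platelets, red blood cells) and/or growth factor support will be reported". The same section also foresees AE incidence calculated cycle by cycle.

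SAP 9.8.1 lists AE tables by SOC, by PT and by maximum CTCAE grade, under the rule "Counting of AEs will be by subject, not by event; subjects will be counted only once within each SOC or PT". On cycles it says: "AEs will not be summarized by Cycle, except for Overall Summary and AEs by SOC and PT for Cycle 1". It defines no grouped term for any cytopenia.

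SAP 9.8.3 covers the laboratory side: "Shift tables for some hematology and chemistry tests will be provided for the maximum post-baseline grade". Scheduled and unscheduled visits up to the end-of-treatment visit are included. The tests are not named in the visible text.

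Protocol 11.4.5 decides which laboratory findings become AEs at all. They do so only with clinical signs or symptoms, when treatment is stopped because of them, or when the investigator judges them medically important. In that case, "the identified medical condition (e.g. low white blood cell count, increased ALT) must be reported as the AE rather than the abnormal value itself".

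SAP 7.2 and 9.5 tabulate concomitant medications. No summary is specific to transfusion or growth factors.

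**The concern.** Haematological events are among the most common adverse events that the protocol gives for this drug, alongside gastrointestinal events and fatigue (Protocol 4.2.3 and 4.3). Treatment is repeated in 28-day cycles, so a reader of the safety results will ask how many subjects reached Grade 3 or 4, in which cell line, and whether the rate rises with continued treatment. The protocol planned tables that answer those questions. The SAP's visible outputs do not produce the by-cycle answer, and leave open whether all three cell lines that the protocol names will be covered overall.

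A second, smaller issue lies in the AE tables. If sites report one cytopenia sometimes as a condition and sometimes as a low count, and the two are coded to different preferred terms, no row shows how many subjects had that cytopenia. A reader who takes one row as the total would then read it too low.

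**Working it through.** **1. Commitments against planned outputs**

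| Protocol 12.1.2 | Nearest visible SAP output | What is missing |
|---|---|---|
| Grade 3–4 haematological incidence by cycle | 9.8.1: overall summary, and SOC/PT counts for Cycle 1. 9.8.3: descriptive values at scheduled visits | Graded incidence per cycle |
| The same across all cycles | 9.8.3: maximum-grade shift tables for unnamed tests. 9.8.1: TEAEs by SOC, PT and maximum grade | A named incidence output, and assurance that neutrophils, platelets and haemoglobin are all covered |
| Transfusion and growth-factor use | 7.2 and 9.5: concomitant medications | A count of subjects with any red-cell transfusion, any platelet transfusion, any growth factor |

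**2. Which source is complete**

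Under Protocol 11.4.5, a Grade 3 or 4 count without symptoms, without discontinuation and not judged medically important is not reported as an AE. It then appears in no table of SAP 9.8.1. The laboratory-graded tables are therefore the fuller source, and the gap in SAP 9.8.3 is the one that matters most. That section also needs clarifying: it speaks of the maximum post-baseline grade and then of each post-baseline time point. Even on the second reading, the result is a grade at each visit for the tests covered, not the proportion of subjects reaching Grade 3 or 4 within a cycle.

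**3. How far term splitting could go (illustration only)**

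No figure in the plan can be reproduced here. Inputs: N = 80 (the planned minimum for AIM-HN) and a subject-level incidence P of 10% or 45%. The 45% is the myelosuppression figure in Protocol 4.4 for a different schedule and dose; the 10% is assumed. Also assumed are two preferred terms, an even split of subjects with only one term, and a share *o* of affected subjects coded to both.

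Affected n = N × P. Each row = o·n + (n − o·n)/2, rounded to whole subjects. A grouped row = n.

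| P (n) | o = 0 | o = 25% | o = 50% | o = 100% | Grouped row |
|---|---|---|---|---|---|
| 10% (8) | 4 and 4 (5.0%) | 5 and 5 (6.25%) | 6 and 6 (7.5%) | 8 and 8 (10%) | 10% |
| 45% (36) | 18 and 18 (22.5%) | 23 and 22 (28.8%, 27.5%) | 27 and 27 (33.8%) | 36 and 36 (45%) | 45% |

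Under an even split, each row shows between half and all of the subject-level rate. Laboratory-graded counts are not affected.

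**4. The table of non-serious TEAEs cut at 5%**

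The cut is 0.05 × 80 = 4 subjects. Two rows can both miss it only if each has at most 3 subjects, so at most 6 are affected (6/80 = 7.5%). With 7 (8.75%), at least one row must appear. If k subjects fall independently into one term or the other and none into both, the chance that both rows are missed is P(k − 3 ≤ X ≤ 3), with X binomial:

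| k | 50:50 wording | 70:30 wording |
|---|---|---|
| 4 | 1 − 2(0.5⁴) = 0.875 | 1 − 0.7⁴ − 0.3⁴ = 0.752 |
| 5 | 20/32 = 0.625 | 0.1323 + 0.3087 = 0.441 |
| 6 | 20/64 = 0.3125 | 20 × 0.343 × 0.027 = 0.185 |

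**The case against.** The strongest reply is that much of the information survives.

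- **Counting rule.** A reader might infer that the SAP's rule departs from the protocol. It does not: Protocol 12.1.2 also counts a subject once per SOC and once per PT, and never promised grouped terms. The rule is how splitting could arise, not a breach, and grouping is an addition.
- **Overall count.** A reader might infer that the SAP abandons the across-cycle Grade 3–4 analysis and counts cytopenias only in single AE rows. The maximum-grade shift tables, with unscheduled draws, can give that count for each test covered, whatever the AE coding. This stands. What remains is that the tests are unnamed.
- **Understated incidence.** Each PT row is correct as defined. The AE tables by SOC and PT carry no stated cutoff, so an event missing from the 5% table still appears there. Splitting needs an assumption about coding that the documents do not settle. The wording in Protocol 11.4.5 (low white cell count) and 12.1.2 (neutropenia) concerns different parameters, so it does not prove that one event will carry two names. With full overlap nothing is lost. Understatement is possible, not shown.
- **Transfusion and growth factors.** Protocol 8.1.4 treats both as supportive care to be recorded, and SAP 7.2 covers medications or treatments, so some of this use should appear there. Only the dedicated summary is absent.
- **Sampling.** Scheduled on-treatment haematology is mainly at Day 1 of each cycle. That limits the protocol's analysis and the proposed one equally, so it is no argument against the SAP.
- **Disclosure.** The items before 4 in SAP Section 3 are blacked out, and the mock tables are in a separate document that may name the tests. It cannot be said that the change is undisclosed.

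None of this supplies a by-cycle graded incidence or a transfusion and growth-factor summary.

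**Conclusion.** The conflict is real but moderate. The by-cycle Grade 3–4 haematological incidence is not in the visible SAP, and 9.8.1 rules out its AE form. The across-cycle incidence is recoverable only for whichever tests the shift tables include. Transfusion and growth-factor use lacks its own summary. These conclusions rest on comparing the texts and need no numerical assumption, except that redacted text or the separate mock tables might fill part of the gap.

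The effect of term splitting in this trial cannot be sized. The illustration assumes the incidence, the wording split and the overlap. It also uses the planned 80 subjects, while SAP Section 3 refers to early closure.

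Two further inferences are tempting. One takes the five Grade 3 myelosuppression events in 21 patients from the alternating-week solid-tumour study in Protocol 4.4 (5/21 = 24%) and projects 19 affected subjects among 80. The source counts events, not patients, in a dose-escalation study, and does not give the doses at which they occurred. The other treats blood toxicity as the drug's principal harm and concludes that the safety objective will be answered too favourably. The protocol lists haematological events together with gastrointestinal events and fatigue, and no direction of bias has been demonstrated.

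**What to change.** - **SAP 9.8.3:** name neutrophils, platelets and haemoglobin. Tabulate the number and percentage of subjects with laboratory-graded CTCAE Grade 3 and Grade 4, overall and by cycle, including unscheduled draws, with subjects starting the cycle as the denominator. State to which cycle a Day 1 sample is assigned, and whether the shift tables use the maximum grade or each time point.
- **SAP 9.8.1:** add pre-listed grouped terms for neutropenia, thrombocytopenia, anaemia and leukopenia, each subject counted once per group, any grade and Grade ≥ 3, alongside the PT rows.
- **Supportive care:** add one row each for any red-cell transfusion, any platelet transfusion and any growth-factor use.
- If any of the protocol's outputs is deliberately omitted, say so and give the reason in SAP Section 3.

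The cost is SAP wording and a few extra tables from data already collected. Reported cytopenia rates may look less favourable. Nothing in the treatment or follow-up of subjects changes.

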## 9.8.2 Deaths

Death data from the survival status CRF will be summarized in a table and presented in a listing. Causes of death will be included.

## 9.8.3 Clinical Laboratory Parameters

Clinical laboratory assessments (hematology and clinical serum chemistry) will be summarized descriptively based on observed values at baseline and each post-baseline scheduled visit and change from baseline. All laboratory results (hematology, clinical serum chemistry, urinalysis, and coagulation) will be reflected in listings.

Shift tables for some hematology and chemistry tests will be provided for the maximum post-baseline grade including data from any scheduled and unscheduled visits prior to or on end of treatment visit. These tables will compare the NCI-CTCAE grade for the baseline value relative to each post-baseline time point value for all non-missing post-baseline data. Subjects meeting shift criteria for high values as well as low values during the course of the trial will be summarized for both criteria.

## 9.8.4 Vital Signs

Body temperature will be summarized in °C. If body temperature is recorded as °F, then temperature will be converted to °C using:

$$\text{Temperature (°C)} = 5/9 (\text{Temperature [°F]} - 32).$$

Summaries of post baseline abnormal vital signs, including systolic blood pressure, diastolic blood pressure, pulse rate, weight change, and temperature will be presented. Abnormal ranges for vital signs parameters are given in [Table 3](#). Post baseline includes non-missing records from both scheduled and unscheduled visits after the first dose of study drug until 30 days following the last dose of study treatment.

**Table 3 Vital Sign Abnormal Values**

Parameter	Abnormal (Low)	Abnormal (High)
Systolic Blood Pressure	Absolute value $\leq$ 90 mmHg for post baseline, or a decrease from baseline $\geq$ 20 mmHg for change from baseline	Absolute value $\geq$ 180 mmHg for post baseline, or an increase from baseline $\geq$ 20 mmHg for change from baseline
Diastolic Blood Pressure	Absolute value $\leq$ 50 mmHg for post baseline, or a decrease from baseline $\geq$ 15 mmHg for change from baseline	Absolute value $\geq$ 105 mmHg for post baseline, or an increase from baseline $\geq$ 15 mmHg for change from baseline
Pulse	Absolute value $\leq$ 50 bpm for post baseline, or a decrease from baseline $\geq$ 15 bpm for change from baseline	Absolute value $\geq$ 120 bpm for post baseline, or an increase from baseline $\geq$ 15 bpm for change from baseline

Sponsor: Kura Oncology, Inc.

Protocol no: KO-TIP-007

Statistical Analysis Plan

Version 1.0 Date: 06-Jun--2023

Weight Change	Weight loss from baseline $\geq 20\%$	
Temperature	$\leq 35^{\circ}\text{C}$ post baseline only	$\geq 40^{\circ}\text{C}$ post baseline only

A listing of vital sign results will also be presented in the Safety Analysis Set.

